## **6.1.2.** Best Overall Response

Best overall response (BOR) is the best response designation recorded for a patient. In determining the best overall response, the overall responses for a patient should be ordered according to descending best response as CR > PR > SD > PD. For example, if a patient had an SD, PR, CR, CR, PD at Cycle 1, 2, 3, 4, and 5 respectively, the best overall response for this patient is CR. Patients who have no post-baseline response assessment data will be considered as non-responders with response category of not evaluated (NE).

To be qualified as BOR, CR and PR require a confirmation at least 4 weeks after initial observation of such response, and SD requires to be observed at least once after 6 weeks (-3 days) from the first dose of study drug.

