5.4. Guidelines for Study Drug Discontinuation

Participants who tolerate study drug may continue to receive the study drug, as specified in the protocol, until any one of the following conditions are met:

- Progressive disease (PD) Objective progression per RECIST v1.1 or clinical progression as determined by investigator
 - Participants who experience PD by RECIST v1.1 should discontinue study drug.
 However, participants who have experienced clinical benefit may continue the treatment if agreed upon between the sponsor and the investigator
- AE requiring study drug discontinuation including, but not limited to, the following events:
 - Study drug-related ≥ Grade 3 cardiac event

- Study drug-related Grade 4 non hematologic event
- DLT during dose-escalation window (DLT period)
- Pregnancy
- Death
- Investigator decision
- LTFU
- Major protocol deviation requiring study drug discontinuation
- Participant declining further treatment
- Participant decision to withdraw consent for study
- The sponsor, investigator, or regulatory agency terminate the study

If the investigator decides that the participant should be withdrawn from the study or from dosing for any reason other than disease progression, the sponsor or its designee must be alerted in a timely manner by completing the appropriate eCRFs.

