8.1.1. Prohibited Therapy

CYP3A4/5 is implicated in the metabolism of DM50 and DM51. Therefore, strong CYP3A inhibitors and inducers, if clinically feasible, should be avoided as concomitant medications for at least 14 days prior to start of treatment and throughout the study or used with caution if critical to the participant's ongoing care. See Appendix 7 for a list of strong CYP3A inhibitors and inducers.

The following rules concerning concurrent treatment(s) apply in this study:

- Any other anti-neoplastic therapies including but not limited to, chemotherapy or other small molecules, biologics, or radiotherapy are not allowed.
 - Anticancer vaccines are considered concomitant cancer therapy and are prohibited from use during the study.
 - Palliative radiation may be allowed for participants who have local symptoms but overall clinical benefit with sponsor approval. Participant needs to pause study drug during the radiation and may resume the treatment after radiation related adverse events return to baseline. The restart of treatment requires the approval from sponsor.
- Participants may not receive other investigational drugs during the period of study participation.
- Use of corticosteroids should be limited to the extent possible (except as specified in this protocol).
- Primary prophylactic use of G-CSF, granulocyte-macrophage colony stimulating factor (GM-CSF), or other growth factors is prohibited during the first cycle of study drug. Use of growth factors with successive cycles of study drug may be considered on a case by case basis in consultation with the sponsor.
- Inactivated annual influenza vaccination and COVID-19 vaccination are allowed and the sponsor recommends they be administered no less than 5 days before or after the dose of study drug, when feasible, to avoid overlapping AEs.

IMGC936 ImmunoGen, Inc Clinical Study Protocol: IMGC936-0901 Amendment 3 29 March 2022

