9.9. Radiographic, CT, or MRI Assessments

Tumor assessments are performed according to the schedule in Appendix 1 and Appendix 2. Baseline tumor imaging consists of a CT/MRI scan with contrast, unless medically contraindicated, to document tumor burden. Subsequent tumor assessments on study should use the same imaging modality as that for the baseline assessment.

Tumor assessments are performed every 6 weeks (Q6W; \pm 7 days) on Schedule A and every 8 weeks (Q8W; \pm 7 days) on Schedule B while on study drug then every 12 weeks (Q12W; \pm 21 days). Tumor assessments continue until discontinuation criteria are met. Tumor assessments are performed at EOTV except if prior assessment was \leq 30 days of EOTV and results are available for RECIST v1.1 assessment.

CT or MRI scan of the brain will be performed when clinically indicated (eg, history or suspicion of brain metastases) and repeat brain scans will be performed only if the screening brain scan was positive, or as clinically indicated.

If feasible, participants who discontinue study drug for reasons other than PD (eg, toxicity) should continue to undergo tumor assessments Q12W until evidence of PD, initiation of another anticancer therapy, withdrawal of consent, LTFU, death, or end of study whichever occurs first.

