9.15.2. Response Assessments

Tumor assessments (eg, CT scans) will occur after participant has discontinued study drug Q12W (± 21 days) until evidence of progressive disease, initiation of another anticancer therapy, withdrawal of consent, LTFU, death, or end of study, whichever occurs first (Appendix 1 and Appendix 2).

• For RECIST v1.1, the overall responses will be categorized as complete response (CR), partial response (PR), stable disease (SD), PD, or not evaluable (NE) (Appendix 6).

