11. ASSESSMENT OF EFFICACY

11.1. Efficacy Assessments

11.1.1. Disease Response Assessments

Tumor assessments will be obtained using CT and/or MRI scans. Target and non-target lesions will be designated at screening and then evaluated after every other cycle, ie, Q6W (\pm 7 days) on Schedule A and every 8 weeks (Q8W; \pm 7 days) on Schedule B while on study drug (Appendix 1 and Appendix 2). At each tumor assessment time point, the overall response status will be determined based on assessment of target and non target lesions as well as appearance of any new lesions.

If feasible, participants who discontinue study drug for reasons other than PD (eg, toxicity, participant request) should continue to undergo tumor assessments Q12W (\pm 21 days) until evidence of PD, initiation of another anticancer therapy, withdrawal of study consent, LTFU, death, or end of study, whichever occurs first.

• For RECIST v1.1 (Appendix 6), the overall responses will be categorized as CR, PR, SD, PD, or NE. For participants who experience an objective response of CR or PR, responses will be considered unconfirmed until the response has been documented by a subsequent confirmatory scan obtained no less than 4 weeks after the initial scan demonstrating an objective response.

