toxicity is observed during escalation, ocular symptom assessment will occur on Day 1 of each cycle or more frequently if ocular symptoms and signs are observed. Phone-based ocular symptom assessments are acceptable if no clinic visit is scheduled.

- ^h Females of childbearing potential only. Serum pregnancy test is required for eligibility. Subsequent pregnancy tests may use serum or urine. Results must be reviewed before study drug infusion on Day 1 of Cycle 1 and all subsequent cycles. If screening test is performed within 72 hours of first infusion, repeat of the test on Day 1 may be deferred.
- During non-dosing visits (eg, screening and EOTV), vital signs will be taken at one timepoint. For Cycle 1 Day 1, vitals are measured pre-infusion (within 30 minutes before); 15 and 30 minutes after start of infusion (± 5 minutes); EOI (± 10 minutes); and 2, 4, and 6 hours after EOI (± 10 minutes). For Cycle 2 Day 1 and subsequent cycles, vitals are measured pre-infusion (within 30 minutes before), EOI (± 10 minutes), and 1 hour after EOI (± 10 minutes). Participants in dose escalation cohorts must have vital signs recorded on both dosing and non-dosing days through treatment Cycle 3. Beginning on Cycle 4, vital signs must be recorded on Day 1 of each treatment cycle. Participants in expansion cohorts must have vital signs recorded on Day 1 of each treatment cycle.
- ^j To be obtained pre-infusion. Day 1 laboratory samples can be obtained up to 3 days before infusion. Chemistry and hematology results must be reviewed before study drug administration. See Appendix 3 for assessments. Beginning on Cycle 4, laboratory samples only required on Day 1 of each cycle.
- ^k Tumor markers are obtained as indicated for each specific tumor type, eg, CEA for colorectal cancer and CA19-9 for pancreatic cancer. Repeat collection on Cycle 1 Day 1 if screening collection > 7 days prior.
- Tumor assessments are Q6W (\pm 7 days) while participant is on study drug, then Q12W (\pm 21 days). Assessments continue until discontinuation criteria are met. Tumor assessments are performed at EOTV except if prior assessment was \leq 30 days of EOTV and results are available for RECIST v1.1 assessment.
- ^m Tumor assessments will occur after participant has discontinued study drug Q12W (± 21 days) until evidence of PD, initiation of another anticancer therapy, withdrawal of consent, LTFU, death, or end of study, whichever occurs first.

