## **6.1.** Efficacy Outcomes

The response outcomes such as best overall response and overall response rates will be determined based on the response data recorded on the Response and Response Follow-up eCRFs between the date of the first dose of study drug and the date of study discontinuation.

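### Best overall response has no cut at first progression, so a confirmed response seen after PD would count in ORR; separately, the SAP's minimum for stable disease contradicts the protocol

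*SAP*

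**What the plan says.** SAP 6.1 takes BOR and response rates from the response forms completed "between the date of the first dose of study drug and the date of study discontinuation". SAP 6.1.2 then picks the best category: "the overall responses for a patient should be ordered according to descending best response as CR > PR > SD > PD". It adds two conditions: CR and PR must be confirmed at least 4 weeks later, and SD must be seen after a minimum time. Neither refers to progression that came first. The worked example there has PD as the last record, so it does not show what happens when PD comes earlier.

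Protocol Appendix 6, section 2.4 closes the BOR window at the end of treatment. That differs from the SAP, but it is not a cut at progression either.

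Scans after progression can exist. Protocol 5.4 says that PD should stop the drug, then adds: "However, participants who have experienced clinical benefit may continue the treatment if agreed upon between the sponsor and the investigator". Protocol 9.9 schedules scans every 6 weeks on Schedule A and every 8 weeks "on Schedule B while on study drug then every 12 weeks". Once the drug has stopped, Protocol 9.15.2 continues scans only "until evidence of progressive disease, initiation of another anticancer therapy, withdrawal of consent, LTFU, death, or end of study, whichever occurs first".

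On stable disease, SAP 6.1.2 sets the minimum at 6 weeks less 3 days from first dose. Protocol 14.7.1 sets it at 35 days, that is, 6 weeks less 1 week.

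**The concern.** ORR is the primary endpoint of the expansion phase, and it drives the stage 1 decision in each cohort. PFS in SAP 6.1.1 ends at first progression and deals explicitly with alternative anticancer treatment. BOR has no such rule. One participant can therefore be a treatment failure for PFS and a success for ORR on the same scans. Duration of response also fails for that participant. Under Protocol 14.7.3 it ends at the first documented progression, which precedes the response. SAP 6.1.4 does not say which progression is meant.

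The SAP states in 1.1 that it governs the analysis. A programmer who follows 6.1 and 6.1.2 literally counts this participant; one who applies an unwritten convention does not. With 13 or 39 participants per cohort, one classification can matter.

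The SD mismatch is a separate consistency error. It touches the BOR table only.

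**Working it through.** **1. Is there a cut at first PD anywhere?**

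| Place | What it fixes | Cut at first PD? |
|---|---|---|
| SAP 6.1 | Records from first dose to study discontinuation | No |
| SAP 6.1.2 | Rank, confirmation, SD minimum | No |
| SAP 6.1.3 | ORR = number with BOR of CR or PR / population | No |
| Protocol 14.7.1 | Confirmation, SD minimum | No |
| Protocol Appendix 6, 2.4 | Window to end of treatment | No |
| Protocol Appendix 6, Table A-2 | Pairs of time points; no row starts with PD | Silent |

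Table A-1 classifies each time point separately, and PR is measured against the baseline sum (Appendix 6, 2.3.1). An earlier PD in target lesions therefore does not block a later PR.

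**2. The literal result for one illustrative participant (Schedule A).** PD at week 6, drug continued under Protocol 5.4, PR at week 12, PR at week 18.
- BOR = PR, so the participant counts in ORR.
- PFS = event at week 6.
- DoR under Protocol 14.7.3 starts at week 12 and ends at week 6: 6 - 12 = -6 weeks.

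**3. The protocol's design reproduces.** Protocol 14.1 stops at 1 or fewer of 13 and rejects at 7 or more of 39, with rates of 9% and 25%.

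P(reject | p) = sum over x = 2 to 13 of P(Bin(13, p) = x) × P(Bin(26, p) ≥ 7 - x)

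This gives 0.0454 at p = 9% (limit 0.05) and 0.809 at p = 25% (stated 80%). The chance of stopping at stage 1 at 9% is 0.671. The design itself is sound; the question is what counts as a responder in it.

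**4. Effect of one case on the estimate (Clopper-Pearson 95% CI, as SAP 6.2 plans).**

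| Without the case | With the case | Change |
|---|---|---|
| 1/13 = 7.7% (0.2 to 36.0) | 2/13 = 15.4% (1.9 to 45.4) | 1/13 = 7.7 points |
| 6/39 = 15.4% (5.9 to 30.5) | 7/39 = 17.9% (7.5 to 33.5) | 1/39 = 2.6 points |

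**5. How often one case could matter at stage 1.**
- P(exactly 1 of 13) = 13 × 0.09 × 0.91^12 = 0.377 at a true rate of 9%.
- P(exactly 1 of 13) = 13 × 0.25 × 0.75^12 = 0.103 at 25%.

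These are the chances that a cohort sits one responder short. They are not flip rates.

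For a flip rate, let r be the chance that a non-responder has a confirmed post-PD response already recorded at the look. The documents give no value, so r is assumed. With P(0 of 13) = 0.91^13 = 0.2935 at 9%:

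P(flip) = 0.3773 × [1 - (1 - r)^12] + 0.2935 × P(Bin(13, r) ≥ 2)

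| r (assumed) | P(flip) |
|---|---|
| 0.5% | 0.0220 + 0.0006 = 2.3% |
| 1% | 0.0429 + 0.0021 = 4.5% |
| 2% | 0.0812 + 0.0079 = 8.9% |

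If r is instead the rate over the whole follow-up, these figures are upper limits, because an early look misses late cases. On scheduled scans the earliest confirmation is about week 18 on Schedule A (PD 6, PR 12, confirmation 18) and week 24 on Schedule B (8, 16, 24). With one SD scan first, it is week 24 or week 32.

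**6. The SD minimum.**
- SAP: 42 - 3 = 39 days. Protocol: 42 - 7 = 35 days.
- First Schedule A scan: 42 ± 7 = days 35 to 49, which is 15 days.
- The two rules disagree on days 35 to 38 (36 to 39 if the minimum is read as strictly after): 4 of 15 days. This is a share of days, not a reclassification rate.
- First Schedule B scan: 56 ± 7 = days 49 to 63, which passes both rules.

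**The case against.** The strongest reply is that nobody intends the literal reading and that the route to it is narrow.

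- **Intent.** Duration of response presupposes that response comes first, and Table A-2 has no path from PD to PR. That supports the intended reading, but neither is a rule that removes the record, and the SAP gives its own window and ranking.
- **Frequency.** PD normally ends treatment. The exception needs prior clinical benefit and agreement of sponsor and investigator, which fits PD at the very first scan poorly. A persisting new lesion keeps each time point PD. Appendix 6 also lets equivocal progression wait for the next scan, so some apparent PD is never recorded as such. Protocol 9.9 also says that scans go on until discontinuation criteria are met; read literally, that ends them at PD. All this stands: cases should be rare.
- **New therapy.** This route is nearly closed by conduct. While on drug, "Any other anti-neoplastic therapies including but not limited to, chemotherapy or other small molecules, biologics, or radiotherapy are not allowed" (Protocol 8.1.1, with an exception for approved palliative radiation), and off-drug scans stop at new therapy. That stands too.
- **Decision rules.** SAP 4.8 lists no interim analyses, the SAP performs no hypothesis test (4.9, 4.10), and a cohort with 2/13 only may continue. So the 7/39 rule belongs to the protocol alone, and at 39 the effect is on the reported ORR and its interval. The 2/13 rule, however, is restated in SAP 3.3 and 3.4.1 with no other definition of a responder.

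These points limit how often the problem arises. They do not supply the missing cut.

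**Conclusion.** The rule is wrong as written. SAP 6.1 and 6.1.2 would count a confirmed response first seen after PD as an objective response, and no passage in either document prevents it. One case is worth 7.7 points of ORR at 13 participants, where it can reverse a futility stop, and 2.6 points at 39. The frequency is unknown and probably low; the flip rates of 2.3% to 8.9% rest on assumed values of r and are illustrations only. This should be corrected before analysis, but it does not undermine the design. Confidence is medium because the size depends on how often treatment continues past PD, which the documents do not say.

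The SD contradiction is certain and minor. On Schedule A, an SD scan inside the window but before day 39, with no later SD scan, becomes PD or NE under the SAP. So does an unconfirmed PR at such a scan that is followed by PD. ORR is not affected.

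**What to change.** Add to SAP 6.1 and 6.1.2: *BOR is derived only from assessments up to and including the first documented RECIST progression or the start of new anticancer therapy, whichever is first; responses first seen later are listed separately and do not count in ORR or DoR.* This brings BOR into line with the SAP's own PFS rules. The SAP should also say whether palliative radiation approved under Protocol 8.1.1 counts as new anticancer therapy here, and use the same definition for PFS.

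Set the SD minimum in SAP 6.1.2 to 35 days from first dose, as in Protocol 14.7.1.

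Because the SAP governs the analysis, these edits are enough for now. The cost is one sentence, the clarification of new therapy, one number, and the programming. Protocol Appendix 6, section 2.4 should be aligned at the next amendment, since that needs sponsor approval and, where required, ethics approval. The only loss is that a rare response after progression no longer counts in ORR; it stays visible in the listing.

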## 6.1.3. Objective Response Rate (ORR)

The ORR will be calculated as the number of patients with a BOR of CR or PR divided by the number of patients in the corresponding analysis population. Patients without at least 1 post-baseline efficacy assessment will be treated as non-responders and their BORs will be set to NE (not evaluated).

#### 6.1.4. **Duration of Response (DoR)**

DoR is defined only for patients who achieve a response (CR/PR) and will be measured from the

date of initial response to progressive disease or death, whichever occurs first.

Per the BOR definition, patients with an overall response of CR or PR must have a repeat tumor assessment performed no less than 4 weeks after the criteria for response are first met. The first date at which a CR or PR response was noted will be used to calculate DoR, not the date of the confirmatory tumor assessment.

DoR is only defined for responders (ie, patients who have a BOR of CR or PR). The censoring rule for DOR is same as that for PFS. Specifically, the last 3 situations described in Table 2 will be applied. DoR analyses will be performed only if there are enough responders to render the analyses meaningful.

## **6.2.** Efficacy Outcome Analysis

The protocol specifies the following as exploratory analyses:

- To describe antitumor activity of IMGC936 using Response Evaluation Criteria in Solid Tumors version 1.1 (RECIST v1.1)
- To explore progression-free survival (PFS)

The number and percent of participants with their BOR will be presented. The objective response rate (ORR) will be presented together with BOR. Two-sided 95% exact binomial confidence intervals (CIs) of the response rates will be calculated using the method of Clopper—Pearson.

Percent change of tumor size from baseline over time will be summarized and presented by spider plot. The tumor size is defined as the sum of diameters of the target lesions. The best percent change of tumor size from baseline will be presented by waterfall plot.

The Kaplan-Meier method will be applied to estimate PFS and DoR curves; their median times, and PFS rates at 3 and 6 months, respectively. The method of Brookmeyer and Crowley will be used to construct 95% CIs for median time. The 95% CIs for PFS rates at each time point of interest will be calculated by normal approximation after log(-log) transformation.

# **6.3.** Other Exploratory Efficacy Analyses

The exploratory analyses on the relationship of immunogenicity, biomarker and PK with antitumor activity will be covered by a separate, independent analysis plan.

# **6.4.** Efficacy Analysis on Subgroups of Patients

No subgroup efficacy analysis will be planned.

# 6.5. Additional Sensitivity Analyses

Not applicable.

# **6.6.** Other Efficacy-related Summaries

A listing of new anti-cancer therapies will be provided.

#### 7. SAFETY ANALYSES

The safety analyses will be performed on the Safety population. The assessments/events up to 30 days (inclusive) of the last dose of study drug or prior to the start of a new anti-cancer treatment, whichever occurs first, will be analyzed, unless otherwise stated. Baseline is defined as the last non-missing observed measurement prior to the first dose of study drug.

Unless otherwise stated, summaries of safety data will be presented for each dose level of IMGC936, combined RP2P dose (6mg/kg) as well as for overall of all patients in the Safety population.

# 7.1. Exposure

Study treatment attributes to be used in analyses will include the following. Summary tables will be provided for each dose level of IMGC936.

- Number of treatment doses (or cycles) is defined as the number of infusions of IMGC936.
- Treatment duration (weeks) = [(last infusion date first infusion date) + length of cycle] / 7
- Total cumulative dose (mg) = sum of actual dose administered in all cycles while the patient is on study drug
- Actual dose intensity (mg/kg/dose) = total cumulative dose (mg) / baseline weight (kg)/(total treatment duration (weeks) / number of weeks in each cycle)
- Relative dose intensity (%) = actual dose intensity/planned dose intensity\*100%

A listing will be provided with the information from all study drug administration eCRFs over the treatment period.

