**Table 1: IMGC936 Dose Levels: Dose Escalation** 

Cohort	IMGC936 Dose
Cohort 1	0.5 mg/kg
Cohort 2	1.0 mg/kg
Cohort 3	2.0 mg/kg
Cohort 4	4.0 mg/kg
Intermediate Dose	5.0 mg/kg
Intermediate Dose	6.0 mg/kg
Cohort 5	7.0 mg/kg
Cohort 6	10.0 mg/kg
Cohort 7	12.0 mg/kg

Dose escalation will follow standard 3 + 3 design until an MTD or MAD is established. To support the selection of the RP2D, upon agreement between investigators and the sponsor, any dose level not exceeding the MTD may be expanded to a maximum of 15 participants for further evaluation of safety, PK, antitumor activity, to facilitate selection of the RP2D. Intermediate dose levels, not exceeding the MTD, may also be explored.

Participants on Schedule A who are not able to complete the 21-day evaluation secondary to AEs considered unrelated to study drug or any other cause unrelated to study drug are considered unevaluable for safety and toxicity during the DLT evaluation period and may be replaced.

Participants may continue on study drug until disease progression, AE requiring discontinuation, withdrawal of consent, physician decision, or other discontinuation criteria are met.

If recommended by the Cohort Review Committee, in conjunction with the Sponsor, based on emerging safety, tolerability, PK, and preliminary antitumor activity of IMGC936, an alternate schedule (Schedule B) may be explored. Each cycle is 28 days in contrast to Schedule A, which is 21 days. Participants enrolled on Schedule B will receive study drug on Days 1, 8, and 15 of a 28-day cycle for the first 2 cycles. On all subsequent cycles (Cycle 3 and beyond), participants will receive study drug on Days 1 and 8 of a 28-day cycle (Table 3). To potentially reduce ocular or other safety events that may be driven by Cmax (maximum drug concentration after infusion), PK modeling suggests a fractionated weekly schedule would allow reduction in Cmax while maintaining AUC exposure. To reduce participant burden of an indefinite weekly schedule, starting from the third cycle, participants will only receive the study drug in the first 2 weeks in a 4-week cycle. The 3 + 3 dose escalation as described previously will apply to the alternate schedule. The recommended starting dose of 2 mg/kg/dose (Cycles 1 and 2) and 3 mg/kg/dose (Cycle 3 and beyond) for Schedule B in a 4-week cycle is less than the non-fractionated total dose of 7 mg/kg every 3 weeks, which was administered in Cohort 5 of Schedule A.

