Table 3: IMGC936 Dose Levels: Dose Escalation (Schedule B)

Cohort	IMGC936 Dose on Days 1, 8, and 15 of Cycle 1 and Cycle 2	IMGC936 Dose on Days 1 and 8 of Cycle 3 and beyond	
Cohort B1	2 mg/kg/dose	3 mg/kg/dose	
Cohort B2	2.5 mg/kg/dose	3.5 mg/kg/dose	
Cohort B3	3.0 mg/kg/dose	3.5 mg/kg/dose	
Cohort B4	3.5 mg/kg/dose	4.0 mg/kg/dose	

Upon agreement between investigators and the sponsor, intermediate dose levels may be evaluated based on review of cumulative safety and PK data.

Participants on Schedule B who are not able to complete the 28-day evaluation secondary to AEs considered unrelated to study drug or any other cause unrelated to study drug are considered unevaluable for safety and toxicity during the DLT evaluation period and may be replaced.

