#### 3.5. Interventions

IMGC936 is administered by IV infusion. The drug product is diluted in a solution of sterile Dextrose 5% in Water (D5W), United States Pharmacopeia (USP) in an IV bag for administration with an infusion pump.

IMGC936 is administered on Day 1 of each 21-day cycle. It is expected that Day 1 of subsequent cycles will be no more than 3 days after the previous cycle. IMGC936 is administered as an IV

infusion at the assigned dose for each cohort. Infusion duration will vary depending on dose and participant tolerability.

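### SAP 7.1 treatment duration is 7 or 14 days too long on Schedule B when the last infusion is a Day 8 or Day 15 dose, which lowers relative dose intensity; separately, dose intensity is computed per cycle but labelled per dose

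*SAP*

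**What the plan says.** SAP 7.1 defines the exposure variables once, with no distinction between schedules:

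- Duration: "Treatment duration (weeks) = [(last infusion date first infusion date) + length of cycle] / 7". I read a minus sign between the two dates.
- Actual intensity: "Actual dose intensity (mg/kg/dose) = total cumulative dose (mg) / baseline weight (kg)/(total treatment duration (weeks) / number of weeks in each cycle".
- Relative intensity: "Relative dose intensity (%) = actual dose intensity/planned dose intensity", times 100. Planned dose intensity is not defined.
- Count: "Number of treatment doses (or cycles) is defined as the number of infusions of IMGC936".

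SAP 3.5 describes a single pattern of administration: "IMGC936 is administered on Day 1 of each 21-day cycle". SAP 3.2, however, also provides that "an alternate schedule (Schedule B) may be explored". There, "Participants enrolled on Schedule B will receive study drug on Days 1, 8, and 15 of a 28-day cycle for the first 2 cycles". For later cycles, the Schedule B dose table (Table 3 in SAP 3.2) has a column headed "IMGC936 Dose on Days 1 and 8 of Cycle 3 and beyond". SAP 3.4.1 allows up to 27 escalation participants on Schedule B, and SAP 3.3 allows any expansion cohort to use either schedule.

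**The concern.** The duration formula credits the participant with a full cycle of treatment time after the last infusion. That suits a regimen with one infusion at the start of each cycle. When the last infusion falls on Day 8 or Day 15, one or two weeks of the cycle have already passed, and the formula counts them twice. Duration is the divisor of actual dose intensity, so a participant who received every planned dose on time appears under-dosed.

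Two further gaps sit in the same lines. Dividing by the number of cycles gives mg/kg per cycle, while the printed unit is mg/kg/dose. The two agree with one infusion per cycle and differ with two or three. With planned dose intensity undefined, two programmers could follow the text and report different percentages. The infusion count is also labelled as a cycle count, so two full Schedule B cycles would show as 6.

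At stake is how the Schedule B exposure tables read, especially beside those for Schedule A. The distortion is largest for participants who stop after one or two cycles.

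**Working it through.** The documents state no exposure figure to reproduce, so Schedule A serves as the baseline check.

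**Inputs.** Cycle lengths are 21 days (A) and 28 days (B) (SAP 3.1). Schedule B dosing days are 1, 8 and 15 in Cycles 1 and 2, then 1 and 8 (SAP 3.2). Cohort B1 receives 2 mg/kg/dose in Cycles 1 and 2 and 3 mg/kg/dose from Cycle 3 (Table 3 in SAP 3.2), so 3 × 2 = 6 and 2 × 3 = 6 mg/kg per cycle throughout. Assumptions: full on-time dosing, stable weight, and 1 to 6 completed cycles. The documents do not fix the number of cycles.

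**Schedule A check.** For *n* cycles, duration = [21(*n* − 1) + 21]/7 = 3*n* weeks: 3, 6 and 18 weeks for 1, 2 and 6 cycles. Relative dose intensity is 100%. The formula is exact here.

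**Duration on Schedule B.** With the first infusion as day 0, the last infusion falls on day 28(*n* − 1) + 14 for *n* ≤ 2 and 28(*n* − 1) + 7 for *n* ≥ 3. SAP duration = (that day + 28)/7. True duration, to the end of the last cycle, is 4*n* weeks.

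**Relative dose intensity, B1, per-cycle plan.** Actual = 6*n*/(SAP weeks/4); planned = 6 mg/kg per cycle.

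| Cycles | SAP weeks | True weeks | Actual (mg/kg/cycle) | Relative intensity |
|---|---|---|---|---|
| 1 | (14 + 28)/7 = 6 | 4 | 4.00 | 67% |
| 2 | (42 + 28)/7 = 10 | 8 | 4.80 | 80% |
| 3 | (63 + 28)/7 = 13 | 12 | 5.54 | 92% |
| 4 | (91 + 28)/7 = 17 | 16 | 5.65 | 94% |
| 5 | (119 + 28)/7 = 21 | 20 | 5.71 | 95% |
| 6 | (147 + 28)/7 = 25 | 24 | 5.76 | 96% |

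The figure is 98% at 12 cycles and 99% at 24. If the last infusion is a Day 1 dose there is no error: Cycle 1 gives 28/7 = 4 weeks.

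**Partly dosed last cycle, B1, per-cycle plan.** Last infusion on Cycle 1 Day 8: SAP (7 + 28)/7 = 5 weeks and 4/(5/4)/6 = 53%; corrected, 4 weeks and 4/(4/4)/6 = 67%. Cycle 2 Day 15 omitted, as Protocol Appendix 2 permits: SAP (35 + 28)/7 = 9 weeks and 10/(9/4)/6 = 74%; corrected, 8 weeks and 10/(8/4)/6 = 83%.

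**Unit mismatch, shown separately.** Suppose the plan is taken in mg/kg/dose as the mean planned dose to date: 2, 2, 2.25, 2.4, 2.5 and 2.57 mg/kg for 1 to 6 cycles. The SAP formula then reads 200, 240, 246, 235, 229 and 224%. With the duration corrected it would read 300, 300, 267, 250, 240 and 233%. The mismatch pushes the figure above 100%; the duration error pulls it down.

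**Undefined plan, B3 after 6 full cycles.** The plan is 3 × 3 = 9 mg/kg per cycle, then 2 × 3.5 = 7. Total 2 × 9 + 4 × 7 = 46; actual 46/(25/4) = 7.36. Against the average plan (46/6 = 7.67) this is 96%, against 9 it is 82%, and against 7 it is 105%.

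**The case against.** The best defence is that the formulas were written for Schedule A, where both the duration and the unit label are right. Schedule B is optional, SAP 3.5 describes only Day 1 dosing of 21-day cycles, and the combined safety summary in SAP 7 is for 6 mg/kg, a level in Table 1 but not a per-dose level in Table 3 of SAP 3.2. The tables are descriptive, and the administration listing shows the data without these formulas. All of that stands and limits the importance of the point. It does not remove the error: the same SAP plans for Schedule B in escalation and expansion, and gives no other exposure rule for it.

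A ratio of actual to planned intensity is also naturally read like for like, which makes the per-cycle reading the more plausible one. I agree; the 200 to 246% range is conditional on taking the printed unit literally.

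Two stronger readings are tempting and not supported. A reader might infer that the duration error itself can inflate relative dose intensity, or that its direction depends on the plan chosen. It cannot and does not: a longer duration lowers the result under any plan. A reader might also arrive at 288% after six cycles (5.76/2). That holds the plan at 2 mg/kg/dose throughout, whereas Table 3 in SAP 3.2 plans 3 mg/kg/dose for B1 from Cycle 3; the figures are then 224% against the mean planned dose or 192% against 3 mg/kg.

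**Conclusion.** The duration rule is wrong as written for Schedule B: 14 days too long after a Day 15 dose, 7 after a Day 8 dose, and exact after a Day 1 dose. For fully dosed B1 participants, relative dose intensity runs from 67% (1 cycle) to 96% (6 cycles) on a per-cycle plan, instead of 100%. The other Schedule B cohorts give the same percentages if the plan is averaged over the cycles started.

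The per-dose label and the undefined plan are separate defects with their own effect. These figures assume on-time dosing, stable weight, and treatment time counted to the end of the last cycle started, which is the convention that the formula follows on Schedule A.

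The point is minor. It arises only if Schedule B is opened and touches only descriptive exposure tables. Schedule A duration and unit are unaffected, and nothing in the documents shows an effect on the DLT, adverse event or RP2D outputs.

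**What to change.** In SAP 7.1:

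1. Define duration as (last infusion date − first infusion date + days from that infusion's scheduled cycle day to the end of the cycle)/7. The added term is 21 days on Schedule A, as now, and 28, 21 or 14 days on Schedule B after a Day 1, Day 8 or Day 15 dose. Delays still count: one B1 cycle with Day 15 given 21 days late gives (35 + 14)/7 = 7 weeks and 6/(7/4)/6 = 57%.
2. Label dose intensity mg/kg/cycle.
3. Define planned dose intensity as the average planned mg/kg per cycle over the cycles started, taken from the SAP 3.2 dose tables (Table 1 for Schedule A, Table 3 for Schedule B).
4. Report infusions and cycles as separate counts.

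Protocol 14.4 defines dose intensity as administered over intended dose. Reconciling that with the SAP is a separate matter; the ratio alone would read 6/6 = 100% in the delay example. A note that the formula divides by baseline weight, so the result also moves when doses are recalculated for weight change, is optional.

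The cost is SAP wording and programming only.
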